Amendment 2, Version 1.0	20Apr2020	
 - Phase 1b Dose Level changes per new available data - Protocol revisions per Atezolizumab IB v15, July 2019 and Atezolizumab IB v15 Addendum 2, December 2019 - Protocol revisions per NT-I7 IB v5, January 29, 2020 - Administrative corrections 	
Amendment 3, Version 1.0	23Apr2021	
 - Protocol revisions per Atezolizumab IB v17, September 2020 - Protocol revisions per NT-I7 IB v6, February 19, 2021 - Added 2 timepoints for Serum Chemistry in Study Calendar Table - Corrected Chemical formula and Structural formula for NT-I7 - NT-I7 dosing schedule changed from Q3W to Q6W (every other cycle) per new available data - Pharmacokinetic draw schedule modified per new available data - Administrative corrections 	
Amendment 4, Version 1.0	11MAR2022	
 - Protocol revisions per Atezolizumab IB v18, July 2021 and Atezolizumab IB v18 Addendum 1, August 2021 - Changed irRC to iRECIST - Clarification to Exclusion Criteria - Added notes, clarification to current protocol language - Administrative corrections 	
Amendment 5, Version 1.0	19JAN2023	- Updated RP2D to 1200 µg/kg	

		
- Protocol revisions per NT-I7 IB v8.0, 19SEP2022- Protocol revisions per Atezolizumab IB v18, July 2021 and Addendum 1, August 2021- Protocol revisions per Dear Investigator Letters, dated July 27, 2022 and November 21, 2022- Administrative corrections and additions	
--	--	--	--

TABLE OF CONTENTS

TABLE OF CONTENTS.....	6
TABLE OF TABLES	8
1. PROTOCOL SUMMARY.....	9
1.1 Synopsis.....	9
1.2 Schema.....	10
2. INTRODUCTION.....	12
2.1 Study Rationale.....	12
2.2 Background - Study Disease(s).....	13
2.3 Agent(s).....	15
2.4 Overall Risk/Benefit and Ethical Assessment.....	19
3. OBJECTIVES AND ENDPOINTS.....	20
4. PATIENT SELECTION.....	22
4.1 Inclusion Criteria	22
4.2 Exclusion Criteria	25
4.3 Inclusion of Women and Minorities	29
5. STUDY DESIGN.....	30
5.1 Overall Design.....	30
5.2 Dose Escalation (Phase 1b).....	31
5.3 Expansion Phase (Phase 2a).....	34
5.4 Other Procedures: Biopsy (core needle, punch or surgical excision).....	35
5.5 Contraception.....	35
6. STUDY TREATMENT.....	36
6.1 Study Treatments Administration.....	36
6.2 Dose-Limiting Toxicity.....	41
6.3 General Concomitant Medication and Supportive Care Guidelines.....	43
6.4 Duration of Therapy.....	45
6.5 Study Treatment beyond Disease Progression.....	46

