6.4 Duration of Therapy

In the absence of treatment delays due to AE(s), treatment with atezolizumab and NT-I7 may continue for *up to 2 years* relative to the date of the 1st dosing or until one of the following criteria applies:

- Disease progression warranting alternative systemic therapy,

Note: Patients with RECIST-defined progressive disease (PD) who are otherwise stable without symptomatic progression may continue study treatment until the next radiographic imaging time point (no less than 4 weeks after the prior assessment of PD) to assess for possible pseudo-progression.

- Intercurrent illness that prevents further administration of treatment,
- Unacceptable AE(s),
- Patient decides to withdraw from the study,
- General or specific changes in the patient's condition render the patient unacceptable for further treatment in the judgment of the investigator,
- Patient noncompliance,
- Dosing interruption lasting >12 weeks (see Section [7.1.1](#)),
- Pregnancy
 - All women of child-bearing potential should be instructed to contact the investigator immediately if they suspect they might be pregnant (e.g., missed or late menstrual period) at any time during study participation.

- The investigator must immediately notify the ION Coordinating Center in the event of a confirmed pregnancy in a patient participating in the study.
- Termination of the study by sponsor(s), or
- The drug manufacturer can no longer provide the study agent

The reason(s) for protocol therapy discontinuation, the reason(s) for study removal and the corresponding dates must be documented in the CRF.

All patients who tolerate the protocol regimen and with either CR, partial response (PR) or SD will be permitted to continue study treatment until confirmed disease progression or for up to 2 years. Patients in response will have the option of continuing on atezolizumab using commercially purchased agent.

Discontinuation of treatment may be considered, at the discretion of the treating physician, for patients who have attained a confirmed CR that have been treated for at least 24 weeks with study treatment and had at least 2 treatments beyond the date when the initial CR was declared.

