4.2. General Statistical Methods and Data Handling

4.2.1. General Methods

All output will be incorporated into RTF or PDFs, sorted and labeled according to the International Conference on Harmonisation (ICH) recommendations, and formatted to the appropriate page size(s).

Phase 1b/dose escalation will be presented by dose levels 120 µg/kg, 360 µg/kg, 840 µg/kg, 1200 µg/kg and Total. Phase 2a/dose expansion will be summarized under the 1200 µg/kg dose. Efficacy analysis will analyze two groups of pooled data. The first group will pool 120 µg/kg, 360 µg/kg, and 840 µg/kg doses levels of Phase 1b; and the second group will pool the 1200 µg/kg dose level from both phases.

For categorical variables, summary tabulations of the number and percentage within each category (with a category for missing data) of the parameter will be presented.

Continuous variables will be summarized using mean, standard deviation, median, inter-quartile range (IQR) and range; 95% confidence intervals will be presented where appropriate.

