4.11.1. Adverse Events

Adverse events will be coded using the Medical Dictionary for Regulatory Activities (MedDRA) and displayed in tables and listings using System Organ Class (SOC) and Preferred Term (PT). AE severity will be graded according to the CTCAE v5.0.

Analyses of adverse events will be performed for those events that are considered treatment emergent, where a treatment emergent adverse event (TEAE) is defined as any adverse event with an onset date on or after the administration of study treatment through the end of the study (defined as 30 days after the last dose of study treatment) or any event that was present at baseline but worsened in intensity or was subsequently considered drug-related by the investigator through the end of the study.

The number and percentage of patients with any TEAE will be reported, TEAEs with CTCAE Grade 3 or Higher, TEAEs assessed by the Investigator as related to treatment (definite, probable, or possible relationship), Treatment-related TEAE with Grade 3 or Higher, TEAEs leading to NT-17/atezo Interrupted (also Dose Reduced and Withdrawn), Adverse Events of Special Interest (AESI; as designated by the CRF), Serious TEAEs, Serious Treatment-related TEAE, and TEAEs leading to Death; summarized by SOC and PT. In these tabulations, each patient will contribute only once in each category regardless of the number of events.

No formal hypothesis-testing analysis of adverse events incidence rates will be performed.

All adverse events occurring on study will be listed in by-patient listings.

By-patient listings also will be provided for the following: patient deaths and serious adverse events.

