5. CHANGES TO PLANNED ANALYSES

Due to the premature closure of the study the following changes are made in comparison to the protocol:

- AEs leading to withdrawal and DLTs will not be listed separately.
- Laboratory values will only be listed.
- irRC (iRECIST) will not be summarized.
- Efficacy summaries will be performed on Efficacy Population only.
- All phases will be summarized within the same table.
- Duration of Stable Disease will replace Duration of Response analysis, due to limited patient responses.

Sponsor:	NeolimmuneTech, Inc.		
Protocol:	NIT-106 (ION-02)		
Document Version No.:	1.0	Document Date:	20Nov2023

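### Adverse-event percentages ignore observation time, and premature closure may have left Phase 2a patients observed for less time than the earlier dose cohorts

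*SAP*

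**What the plan says.** **Metric.** SAP 4.11.1: "The number and percentage of patients with any TEAE will be reported", with the same summary for Grade 3 or higher, related, serious, special-interest, fatal and treatment-modifying events. The counting rule is "In these tabulations, each patient will contribute only once in each category regardless of the number of events".

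**Window.** A TEAE counts if its onset falls between first administration and a point tied to the patient's own last dose: "through the end of the study (defined as 30 days after the last dose of study treatment"). Protocol 6.4 sets the outer limit: "treatment with atezolizumab and NT-I7 may continue for *up to 2 years* relative to the date of the 1st dosing". Progression, toxicity or withdrawal can end treatment sooner.

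**Layout.** SAP 4.2.1: "Phase 1b/dose escalation will be presented by dose levels 120 µg/kg, 360 µg/kg, 840 µg/kg, 1200 µg/kg and Total". The same section places Phase 2a under 1200 µg/kg. SAP 5 adds: "All phases will be summarized within the same table". It does not say whether Phase 2a and the Phase 1b 1200 µg/kg cohort share a column.

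**Closure.** SAP 5 opens its list of changes with: "Due to the premature closure of the study the following changes are made in comparison to the protocol". It gives no date.

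**Exposure.** SAP 4.7 summarises dose intensity by phase and dose level or arm, and the number of patients completing each cycle. No AE table uses either.

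**The concern.** A percentage that counts each patient once rises with time observed. If one column is watched for less time than another, it will show fewer patients with an event even when the underlying rates are equal. The 3+3 design fills dose levels in sequence and Phase 2a comes last, so early closure would tend to shorten the windows of the patients enrolled last.

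Nothing else in the planned safety output corrects for this. Dose intensity is total dose divided by treatment duration, so it divides out the very quantity that may differ. Cycles completed would reveal unequal exposure but adjusts no AE percentage. The dose-limiting toxicity (DLT) period is 21 days at every dose level, but SAP 4.11.1 names no DLT table and SAP 5 drops the separate DLT listing. The crude table is therefore the main published safety profile of the combination, in a trial whose Phase 1b primary objective is safety and tolerability.

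**Working it through.** The plan states no AE rate or observation time, so there is no figure of its own to reproduce. The check asks how large the effect could be.

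**Dates (documents)**
- Amendment 5, which records the RP2D as 1200 µg/kg: 19 Jan 2023.
- Amendment 3, 23 Apr 2021: "NT-I7 dosing schedule changed from Q3W to Q6W (every other cycle) per new available data". Protocol 5.2.1 starts every-6-week dosing at 1200 µg/kg, so the 120–840 µg/kg cohorts are taken to have started by then.
- SAP: 20 Nov 2023, taken as the latest possible closure.
- Amendment 5 to SAP: 305 days / 30.4375 = 10.0 months.
- Amendment 3 to SAP: 941 days / 30.4375 = 30.9 months, which exceeds the 24-month maximum.

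These are document dates standing in for enrolment dates. They bound the longest possible window and do not measure the actual one.

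**Assumptions**
- The same constant hazard h = 0.05 per month at every dose.
- Exponential time on treatment, λ = ln 2 / median.
- A tail of t = 30 / 30.4375 = 0.986 months after the last dose.
- An administrative cap c on treatment: 24 months for the early cohorts. For Phase 2a, either 10.0 months for everyone (best case) or uniform on 0 to 10.0 months (steady entry from Amendment 5).

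**Formula**

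P(c) = 1 − e^(−ht) × [ λ/(λ+h) × (1 − e^(−(λ+h)c)) + e^(−(λ+h)c) ]

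For steady entry, P(c) is averaged over c. Share missed = 1 − P(Phase 2a) / P(24).

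**Example, median 6 months**
- λ = 0.1155, λ+h = 0.1655, λ/(λ+h) = 0.698, e^(−ht) = 0.952.
- c = 24: 1 − 0.952 × (0.698 × 0.981 + 0.019) = 33.0%.
- c = 10.0: 1 − 0.952 × (0.698 × 0.810 + 0.190) = 28.1%.
- Share missed = 1 − 28.1/33.0 = 15%.

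| Median time on treatment | Early cohorts, cap 24 | Phase 2a, cap 10.0 | Missed | Phase 2a, steady entry | Missed |
|---|---|---|---|---|---|
| 2 months | 16.8% | 16.6% | 1% | 13.8% | 18% |
| 3 months | 21.7% | 20.7% | 5% | 16.1% | 26% |
| 4 months | 26.0% | 23.8% | 8% | 17.6% | 32% |
| 6 months | 33.0% | 28.1% | 15% | 19.5% | 41% |
| 9 months | 40.5% | 31.8% | 22% | 21.1% | 48% |

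**If Phase 2a opened before Amendment 5.** Steady entry over 16 months gives 17%, 22%, 29% and 35% missed at medians of 3, 4, 6 and 9 months. Over 22 months it gives 12%, 16%, 22% and 27%. At a 2-month median the figures are 11% and 8%.

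**Phase 1b cohort at 1200 µg/kg.** With entry uniform between Amendments 3 and 5, the available time is 10.0 to 30.9 months, capped at 24. The share missed is 0.7%, 1.5%, 3.2% and 5.2% at medians of 3, 4, 6 and 9 months.

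**Early-onset events.** If an event type occurs only in the first weeks, nearly every patient is observed through the risk period and the share missed is near zero.

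**Precision.** Exact 95% intervals are 0–70.8% for 0/3 and 0.4–64.1% for 1/6.

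**The case against.** The strongest objection is that the documents do not show unequal follow-up. They give no closure date, Phase 2a opening date or time on treatment by dose. Amendment 5 records a dose update, not the start of enrolment. Because the window follows treatment, early progression in all cohorts would bring the windows close together, and SAP 5 mentions limited responses, which makes the long-median rows less likely. This stands, and it is why the point is put as something that may have happened. A reader might infer that Phase 2a was in fact watched for much less time and that the selected dose looks safer than it is. The documents support neither statement.

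A reader might also infer that the dose decision is compromised. It is not. Protocol 5.2.2 bases escalation on the fixed 21-day DLT window and the RP2D on that plus T-cell effect, and the RP2D was recorded ten months before the SAP.

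Unequal exposure would also be partly visible from SAP 4.7 and the by-patient listings, and no hypothesis tests are planned. That is true, but visibility is not adjustment, and readers compare adjacent columns whether or not there is a p-value.

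Finally, cohorts of 3 or 6 cannot rank doses under any metric, and the columns differ in NT-I7 schedule (every 3 versus every 6 weeks). Both hold. They are further reasons for caution with the crude columns, and they limit what the added tables can show.

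Amendment 3 also added two serum chemistry timepoints, which could raise laboratory AE detection in later patients. The log does not identify the visits, so no adjustment for this can be specified.

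**Conclusion.** The structural point holds: no AE output uses person-time or a common window, dose levels and phases sit in one table, and the study closed early. Whether this distorts the Phase 2a percentages, and by how much, cannot be settled from the documents.

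Under the stated assumptions, the share of Phase 2a patients with an event that is missed, relative to cohorts able to complete 24 months, runs from about 1% (2-month median, everyone with 10 months available) to 48% (9-month median, steady entry). The range depends mainly on time on treatment and entry pattern, neither of which is reported. The direction, if windows are shorter, is towards lower percentages in Phase 2a. Within Phase 1b the comparison involving 1200 µg/kg is barely touched (about 1–5% at medians of 3 to 9 months). If the two 1200 µg/kg groups share a column, the Phase 1b patients would dilute any effect.

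This is a worthwhile and inexpensive improvement to safety reporting. It is not evidence of a biased result.

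**What to change.** In SAP 4.11.1, keep the crude table and make these changes:

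- Show Phase 2a in its own column, apart from Phase 1b at 1200 µg/kg.
- Give median time on treatment and total patient-months of TEAE observation for every column.
- For the TEAE categories already listed, add incidence in a common early window, for example Cycle 1 Day 1 to Day 42. The denominator is patients observed to Day 42 or with an earlier event, with the number left out shown.
- For the same categories, add patients with a first event per 100 patient-months at risk, with an exact Poisson 95% confidence interval. For d patients with an event in T patient-months, the limits are χ²(0.025; 2d)/(2T) and χ²(0.975; 2d+2)/(2T), times 100; the lower limit is 0 when d = 0.
- State that any description across dose levels or phases is read from these two additions, with a note on the 3–6 patient cohorts and the schedule difference.

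The cost is two more table shells, built from dates already collected, with no new patients or data. There are three limitations. Intervals in the small cohorts will be wide. The patient-month rate assumes a roughly constant hazard, which the early-window table offsets. The early-window denominator leans slightly upward: a patient dosed only on Day 1 is counted to Day 31 and drops out if event-free, whereas one dosed again on Day 22 is counted to Day 52.

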4.11.2. Laboratory Data

A listing of all laboratory data will be generated; normal ranges and CTCAE grades will be included. A subset listing will be presented for all notable abnormal laboratory values.

Complete Blood Count (CBC) parameters include: White Blood Cells (WBC), Red Blood Cells (RBC), Hemoglobin, Hematocrit, Platelets, Absolute Neutrophil Count (ANC), Absolute Lymphocyte Count (ALC), Absolute Eosinophil Count, Absolute Basophil Count, Absolute Monocyte Count, Neutrophils, Lymphocytes, Eosinophils, Basophils and Monocytes.

Serum Chemistry parameters include: Albumin, Alkaline Phosphatase, Bilirubin, Bicarbonate, Blood Urea Nitrogen (BUN), Calcium, Chloride, Creatinine, Glucose (Non Fasting), Lactate Dehydrogenase (LDH), Phosphorus, Potassium, Total Protein, Aspartate Aminotransferase (AST or SGOT), Alanine Aminotransferase (ALT or SGPT), Sodium, Lipase, Amylase, TSH.

Sponsor:	NeolimmuneTech, Inc.		
Protocol:	NIT-106 (ION-02)		
Document Version No.:	1.0	Document Date:	20Nov2023

4.11.3. Vital Signs and Physical Examinations

The value and change from baseline at each time point will be summarized for vital signs, including systolic and diastolic blood pressure, heart rate, respiratory rate, and temperature.

By-patient listings of vital sign measurements will be presented in data listings.

All physical examination findings will be presented in a data listing.

4.11.4. Electrocardiogram

All ECG data for each patient will be provided in data listings.

4.11.5. ECOG Performance Status

ECOG data will be listed.

4.11.6. Prior and Concomitant Medications

Prior medications will be defined as all medications taken before the administration of study treatment.

Concomitant medications will be defined as all medications taken on or after the administration of study treatment or within 30 days after the last administration date.

Concomitant medications will be coded using the WHO Drug dictionary. Results will be tabulated by Anatomic Therapeutic Class (ATC) and preferred term.

The use of concomitant medications will be included in by-patient data listing.

Sponsor:	NeolimmuneTech, Inc.		
Protocol:	NIT-106 (ION-02)		
Document Version No.:	1.0	Document Date:	20Nov2023

5. CHANGES TO PLANNED ANALYSES

Due to the premature closure of the study the following changes are made in comparison to the protocol:

- AEs leading to withdrawal and DLTs will not be listed separately.
- Laboratory values will only be listed.
- irRC (iRECIST) will not be summarized.
- Efficacy summaries will be performed on Efficacy Population only.
- All phases will be summarized within the same table.
- Duration of Stable Disease will replace Duration of Response analysis, due to limited patient responses.

Sponsor:	NeolimmuneTech, Inc.		
Protocol:	NIT-106 (ION-02)		
Document Version No.:	1.0	Document Date:	20Nov2023

